### 3.4.2 *Other Efficacy Endpoints*

All other efficacy assessments will be listed. These include the following:

- Changes over time in other laboratory and other parameters related to renal function, including:
  - Serum albumin
  - Creatinine
  - Cystatin C
  - Urine albumin to creatinine ratio (UACR)
  - Total 24 hour urine protein excretion
- Quality of Life endpoints include:
  - Change in factors associated with quality of life from baseline over time as assessed using the SF-36 v2
  - Change in factors associated with quality of life from baseline over time as assessed using the EQ-5D-5L

### 3.4.3 Subgroups

Since analysis will be limited in scope and ITT population will consist of a maximum 13 subjects total, subgroups will not be included in analysis.

## 3.5 Pharmacokinetic Assessment

Dosing and pharmacokinetic sampling times for CCX140 for individual subjects will be summarized in terms of dose, subject, visit, date/time of reference dose, scheduled timepoint, date/time of specimen collection, actual hour relative to reference dose (hr) and deviation from scheduled time. Individual and mean plasma concentrations of CCX140 will be listed, plotted, and summarized descriptively and graphically for subjects receiving CCX140-B.

The following PK parameters of individual subjects and their summary statistics will be determined for CCX140 on Day 1, Day 29 (or 14 days following initial 10 mg BID dosing) and Day 57 (or 14 days following initial 15 mg BID dosing) where possible:

$C_{max}$ : Maximum plasma concentration

$T_{max}$ : Time of maximum plasma concentration

$AUC_{0-6}$ : Area under the plasma concentration-time curve from Hour 0 to Hour 6

$AUC_{0-12}$  on Day 29 and Day 57 will also be estimated assuming that steady state has been achieved, treating the pre-dose concentration also as the 12 hour concentration.

The concentration data of CCX140 as reported by the respective bioanalytical laboratory will be used without rounding for all analysis.

The sample time of the pre-dose samples on Day 1, Day 29 and Day 57 will be uniformly considered as time "0".

For the trough concentration, all missing or below the limit of quantification (BLQ) concentrations will not be imputed and will be excluded from the descriptive summary.

For Day 1, Day 29 and Day 57 visits, individual PK plots or individual PK parameters, since there is no collection window specified for post-dose PK sampling, will be based on actual times recorded. For concentration versus time descriptive statistical summaries and mean plot preparation, nominal time points will be used. If the difference of post-dose sampling time is  $> 5$  minutes from the nominal sampling times for time points  $< 2$  hours or  $> 5\%$  for time points  $\geq 2$  hours, the corresponding concentration data will be excluded from the concentration summary and mean plot preparation, but will still be used in the individual plots and the calculation of PK parameters.

For Day 57 and beyond, the allowable time window for PK trough sampling is  $\pm 3$  hours (i.e., 25% of dosing interval of 12 hours) for 15 mg BID dosing period including the open label extension phase (Day 85 and beyond). If the exact time (measured from dosing) is outside of the collection window, the corresponding concentration will be excluded from trough concentration versus time descriptive statistical summaries.

For the PK blood samples collected at 7 days and 14 days following the last dose of study drug, the actual sampling time should not exceed 5% of the nominal sampling time. If the exact time (measured from dosing) is outside of the collection window, the corresponding concentration will be listed but excluded from descriptive statistical summaries.

### 3.5.1 Pharmacokinetic Concentrations

The individual plasma concentration of CCX140 will be listed.

For subjects with serial samples collected (pre-dose and at 0.5, 1, 2, 3, 4, and 6 hour post-dose after the CCX140-B dose on Day 1, Day 29 (or 14 days following initial 10 mg BID dosing) and Day 57 (or 14 days following initial 15 mg BID dosing):

- Concentration data will be summarized by dose at each nominal time point descriptively;
- Mean ( $\pm$ SD) plasma concentrations of CCX140 will be plotted on a linear scale against nominal time points by dose.

For subjects with sample collected for trough concentration (Day 57 visit and beyond):

- Trough concentration data, within allowable time windows, will be at each visit descriptively.
- Mean trough concentrations (Cmin) of CCX140 will be plotted overlaid with the scatter plot of individual trough concentrations on a linear scale against visits.
- The average steady state trough concentration of CCX140 for each individual subject will be calculated (each subject needs to have at least 3 time points in this steady state period for the calculation). The global average steady state trough concentration of CCX140 will be listed and summarized descriptively.

For subjects with sample collected at 7 days and 14 days following the last dose of study drug,

- Concentration data, within allowable time windows, will be listed and summarized descriptively.

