**Table 1: Dose Modification Schedule and Rules Through Study Day 85**

Study Day	Dose and Requirements for Dose Modification
1	Initiate dosing at 5 mg twice daily
15	At Day 15, dose will be increased to 10 mg twice daily if all of the following are true: 
 
• Subject has not achieved and maintained at least Partial Remission and
 
• Subject is not a Treatment Failure
 

29	At Day 29, PK samples will be collected to measure AUC 0-6 and enable projection of AUC 0-12 at both the current dose level and the next higher planned dose level AUC 0-12
43	At Day 43 based on results of the Day 29 PK, the dose may be adjusted to the next higher planned dose level (15 mg twice daily for subjects receiving 10 mg twice daily; 10 mg twice daily for subjects receiving 5 mg twice daily) if all of the following are true: 
 
• Subject is not a Treatment Failure, and
 
• Meets all criteria for continuation:               
 
○ Subject has not achieved and maintained at least a Partial Remission, and
 
○ Projected AUC0-12 on the next higher planned dose level does not exceed 240 <math>\mu\text{g}\cdot\text{h}/\text{mL}</math> and
 
○ The next higher dose does not exceed the Maximum Tolerated Dose (MTD)
 
 
 
 NOTE: If the projected AUC 0-12 on the current dose exceeds 240 $\mu\text{g}\cdot\text{h}/\text{mL}$ , dose will be de-escalated to the next lower dose level
57	At Day 57, PK samples will be collected to measure AUC 0-6 and enable projection of AUC 0-12
Day 71	Based on results of Day 57 PK, subjects can be considered for dose escalation if all of the following are true: 
 
• Subject is not already treated with 15 mg twice daily and
 
• Subject did not require previous downward dose adjustment and
 
• Subject is not a Treatment Failure, and
 
• Meets all criteria for continuation:               
 
○ Subject has not achieved and maintained at least a Partial
 
 
 

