### **3.3. Dose Modifications During the Extended Treatment Period**

If measured or projected exposure steady state PK exposure ( $AUC_{0-12}$ ) exceeds 240  $\mu\text{g}\cdot\text{h}/\text{mL}$ , which is approximately half of the rat NOAEL  $AUC_{0-24}$ , the dose will be reduced to the dose projected to provide exposure within the target range.

For subjects who escalate dose to 10 mg twice daily on Study Day 15, PK samples from the dose two weeks after 10 mg BID dosing (planned for Day 29) will be analyzed expeditiously and the PK data will be used for projecting the steady state PK exposure. If the projected steady state PK exposure ( $AUC_{0-12}$ ) is higher than 240  $\mu\text{g}\cdot\text{h}/\text{mL}$ , which is half of the rat NOAEL steady state  $AUC_{0-24}$ , the dose will be reduced to 5 mg BID for the remainder of the study ([Table 2](#)).

If the projected steady state PK exposure ( $AUC_{0-12}$ ) is lower than 240  $\mu\text{g}\cdot\text{h}/\text{mL}$ , the steady PK exposure at 15 mg BID will be projected from the 10 mg BID Day 43 PK data. If the projected PK exposure ( $AUC_{0-12}$ ) at 15 BID is lower than 240  $\mu\text{g}\cdot\text{h}/\text{mL}$ , the dose will be escalated to 15 BID. If the projected PK exposure ( $AUC_{0-12}$ ) is higher than 240  $\mu\text{g}\cdot\text{h}/\text{mL}$ , the dose will not escalate to 15 mg BID but will stay at 10 mg BID for the remainder of the study.

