In humans, CCX140-B has been administered and was well tolerated at 15 mg administered once daily for up to 10 days in healthy volunteers, and at 10 mg administered once daily for up to 52 weeks in subjects with Diabetic Nephropathy (DN). Administration of 15 mg twice daily in humans without proteinuria is projected to achieve a peak concentration of ~6.5  $\mu$ g/mL (~13  $\mu$ M) and a trough concentration of ~5.5  $\mu$ g/mL (~11  $\mu$ M) at steady state. Total exposure with 15 mg twice daily is projected to be ~2-fold higher than that achieved with 15 mg daily

administration in healthy volunteers and 3.07-fold higher than that observed with 10 mg daily exposure in subjects with DN. Trough exposure with 15 mg twice daily is projected to be 2.4-fold higher than trough exposure achieved in DN.

The projected clinical exposure with 15 mg BID dosing is 3-fold below the NOAEL exposure established in the most sensitive species tested in the nonclinical toxicity studies (rat 26-week, PO, QD), as detailed in the Investigator's Brochure.

Rationale for selection of 15 mg twice daily is to ensure adequate exposure margin to address:

1. Loss of albumin-bound drug through proteinuria; a post-hoc analysis PK in subjects of trial #CL005\_140 who entered in study with albuminuria >1 gram indicated exposure was approximately 30% below the mean for the treatment group as a whole
2. Increased binding competition from endogenous ligand; MCP-1 is reported to be increased in serum and urine in subjects with FSGS

Rationale for administration of the highest dose as a divided dose (15 mg twice daily), as opposed to a single dose (30 mg once daily) include:

1. Ease of administration (3 tablets twice daily vs 6 tablets once daily)
2. 15 mg administered as a single daily dose has previously been tested and tolerated in healthy volunteers, while 30 mg has not been previously dosed
3. 15 mg twice daily will result in a lower  $C_{max}$  than 30 mg once daily, mitigating the potential for  $C_{max}$ -driven safety concerns

To ensure early detection of dose-related safety signals, the proposed protocol will incorporate:

1. Frequent clinical visits and safety laboratory assessments, including application of a standard health assessment and a questionnaire to detect symptoms of neuropathy at regular intervals as detailed in the [Time and Events Table](#).
2. Safety monitoring by a Safety Review Committee throughout the study.

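### SAP 3.5.1 groups the serial 0–6 h concentrations by dose without occasion, so any steady-state 5 mg BID profile would be averaged with the Day 1 first-dose profiles

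*SAP*

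**What the plan says.** SAP 3.5.1 takes the serial samples from Day 1, Day 29 (or 14 days after 10 mg BID starts) and Day 57 (or 14 days after 15 mg BID starts). For the table it says "Concentration data will be summarized by dose at each nominal time point descriptively". For the figure it says that mean "plasma concentrations of CCX140 will be plotted on a linear scale against nominal time points by dose".

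SAP 3.5 adds: "For concentration versus time descriptive statistical summaries and mean plot preparation, nominal time points will be used". The exclusion rule that follows is split at 2 hours, so a time point there means hours after dosing and does not include the visit. The trough bullets in 3.5.1 do name the visit: "Trough concentration data, within allowable time windows, will be at each visit descriptively".

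Dose follows a rule rather than a fixed calendar. In Protocol Table 1, escalation at Day 15 requires that "Subject has not achieved and maintained at least Partial Remission", and the Day 43 row provides for subjects who are then on 5 mg BID. Protocol 3.3 covers high exposure on 10 mg BID: "the dose will be reduced to 5 mg BID for the remainder of the study". It also provides for subjects who remain on 10 mg BID. Protocol 7.5 (Table 2) resumes treatment one dose level down after certain haematological events.

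**The concern.** On the planned path, dose and occasion coincide: 5 mg is Day 1, 10 mg BID is Day 29 and 15 mg BID is Day 57. Grouping by dose alone is then harmless.

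Off that path, two things can happen. A subject on 5 mg BID at Day 29 or Day 57 has a steady-state profile carrying the same dose label as the Day 1 profiles, which start from a pre-dose level of zero. A mean over both describes no dosing state: too high for a first 5 mg dose, too low for steady state on 5 mg BID, with a wider SD. Separately, a subject still on 10 mg BID at Day 57 may supply two profiles to the 10 mg group.

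Exposure is a stated PK endpoint, and its summaries remain in the abbreviated analysis. With at most 13 subjects, one profile can move a mean visibly.

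**Working it through.** The plan gives no figure to reproduce here, so the check is a trace of the text followed by an illustration of size.

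**Which profiles can share a label**

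| Situation | Day 1 | Day 29 | Day 57 |
|---|---|---|---|
| Escalates on schedule | 5 mg, first dose | 10 mg BID | 15 mg BID |
| Not escalated at Day 15 | 5 mg, first dose | **5 mg BID** | depends on Day 43 |
| Reduced from 10 mg BID by Day 43 | 5 mg, first dose | usually 10 mg BID | **5 mg BID** |
| Held at 10 mg BID | 5 mg, first dose | **10 mg BID** | **10 mg BID**, if sampled |

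The Day 29 profile is unconditional in Protocol Table 1 and 6.4. The Day 57 profile is unconditional in Table 1, Protocol 6.6, the Time and Events Table and SAP 2.3.4. The Synopsis text after Table 1 and Protocol 3.1 tie it to a dose adjustment at Day 43, and Protocol 3.2 ties it to an increase. Under the conditional text, a subject held at 10 mg BID has no scheduled second profile. A subject reduced at Day 43 has had an adjustment, so the Synopsis and 3.1 still call for one.

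**Inputs**
- At 15 mg BID, Protocol 5.2.1 "is projected to achieve a peak concentration of ~6.5" µg/mL and a trough of about 5.5 µg/mL at steady state, without proteinuria.
- Projected AUC0-12 at 15 mg BID: 72 µg·hr/mL (Synopsis, Rationale for Dose Range).
- Subjects: 6 in stage 1, at most 13 in total (SAP 2.2.4).
- Assumed: dose-linear one-compartment kinetics and Tmax of 1 to 4 h, which the documents do not give.

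**Consistency of the inputs.** 12 × (6.5 + 5.5)/2 = 72, which agrees with the stated AUC0-12.

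**Steady state on 5 mg BID.** Peak 6.5/3 = 2.17 and trough 5.5/3 = 1.83 µg/mL.

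**First 5 mg dose.** k = ln(6.5/5.5)/(12 − Tmax), accumulation R = 1/(1 − exp(−12k)), first-dose peak ≈ 2.17/R.

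| Tmax | Half-life | R | First-dose peak (µg/mL) |
|---|---|---|---|
| 1 h | 45.6 h | 6.00 | 0.361 |
| 4 h | 33.2 h | 4.51 | 0.480 |

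**One steady-state profile added to n Day 1 profiles.** Pooled peak = (n × first-dose peak + 2.17)/(n + 1). The relative increase is (R − 1)/(n + 1).

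| n | Pooled peak, Tmax 1 h | Pooled peak, Tmax 4 h | Pre-dose mean |
|---|---|---|---|
| 6 | 0.619 (+71%) | 0.721 (+50%) | 1.83/7 = 0.26 |
| 13 | 0.490 (+36%) | 0.601 (+25%) | 1.83/14 = 0.13 |

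The percentages depend only on R and n. Proportionally lower concentrations in nephrotic subjects would leave them unchanged; a shorter half-life would reduce them.

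**10 mg group.** If m of N subjects have a second 10 mg BID profile at Day 57, the group has N + m profiles. For example, N = 6 and m = 2 gives 8 profiles from 6 subjects.

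**How likely is the exposure route to 5 mg BID?** By linearity, 10 mg BID projects to 72 × 10/15 = 48. The 240 limit is 240/48 = 5 times that.

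**The case against.** The best defence is the parenthesis in the 3.5.1 stem. Naming Day 29 or 14 days after 10 mg BID starts, and likewise for 15 mg BID, can be read as one profile per dose. On that reading nothing is pooled or counted twice. This is a fair reading and it may be what was intended. It still leaves a 5 mg BID profile at Day 29 or Day 57, or a second 10 mg BID profile, without an assigned place.

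Second, two routes to 5 mg BID are narrow. The Time and Events Table schedules the first on-treatment UPCR at Day 15, so a remission that is already maintained can hardly be shown by then. The exposure route needs a fivefold excess over projection, and the protocol expects lower exposure in nephrotic subjects. Both points stand. The safety reductions in Table 2 remain, and Table 1 itself provides for subjects on 5 mg BID at Day 43.

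Third, a reader might infer that the 240 limit or the comparison with the 15 mg BID projection is compromised. The documents do not support that. The limit is applied to each subject's own projected AUC0-12, AUC0-12 is not computed for Day 1, and the 15 mg group contains no first-dose profile.

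Fourth, a reader might infer that the 10 mg n and SD are wrong. SAP 3.1.4 defines n as a count of non-missing values, both profiles come from the same dosing state, and nothing is tested. The n would count profiles rather than subjects, which is a matter of labelling.

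Finally, individual concentrations are listed, so any mixing could be undone, and enrolment has stopped with an abbreviated report planned. That lowers the stakes without settling the grouping.

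**Conclusion.** The concern holds conditionally. Read literally, the rule pools first-dose and steady-state 5 mg profiles if anyone is on 5 mg BID at Day 29 or Day 57. One such profile would raise the 5 mg mean peak by about 50–71% over six Day 1 profiles, or 25–36% over 13, and make the pre-dose mean non-zero. These sizes are illustrations that rest on linear kinetics, the assumed Tmax and rounded projections for people without proteinuria.

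The documents do not say how many subjects leave the schedule. If none does, neither effect occurs, so it cannot be said that the summaries will be mixed. The repeated 10 mg BID profiles are the minor part and depend on which Day 57 sampling text governs.

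The reach is limited to the serial concentration table and mean plot. It extends to Cmax and AUC0-6 in SAP 3.5.2 only in that no grouping is stated there. Efficacy and safety conclusions are not touched.

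**What to change.** In SAP 3.5.1, summarise and plot the serial concentrations by dose and occasion: the Day 1 first 5 mg dose in one group, and steady-state 5, 10 and 15 mg BID each in their own. Use one steady-state profile per subject per dose (for instance the first taken after at least 14 days on that dose) and list the others, or keep all profiles and report the number of subjects beside the number of profiles. Apply the same groups to the parameter summaries in 3.5.2.

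Reconcile the Day 57 sampling text: Table 1, Protocol 6.6, the Time and Events Table and SAP 2.3.4 on one side; the Synopsis text after Table 1 and Protocol 3.1 and 3.2 on the other.

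The cost in the SAP is about two sentences and one grouping variable, with no new data. Some groups may hold only one or two subjects, where a mean and SD add little to the listing.

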### 3.5.2 Pharmacokinetic Parameters

For subjects with serial samples collected (pre-dose and at 0.5, 1, 2, 3, 4, and 6 hour post-dose after the first CCX140-B dose on Day 1, Day 29 (or 14 days following initial 10 mg BID dosing) and Day 57 (or 14 days following initial 15 mg BID dosing), Cmax, Tmax, and AUC0-6 will be determined based on individual CCX140 plasma concentration data. AUC0-12 will be determined for Day 29 and Day 57 assuming pre-dose level being the same as the concentration at the end of the dosing interval.

Parameters	Description
$C_{\max}$	Maximum drug concentration after the first dose; observed directly from the data. If not unique, then the first maximum concentration is used
$T_{\max}$	Time to $C_{\max}$
$AUC_{0-6}$	Area under the concentration-time curve (AUC) from time 0 to 6 hours post-dose. For 6 hours post-dose sample, the corresponding observed concentrations will be used for AUC calculation if the difference of the actual time point is <5% from the nominal time point; otherwise, the concentration at the nominal 6-hour time point will be predicted and then used for the AUC calculation.
$AUC_{0-12}$	AUC from time 0 to 12 hours post-dose on Day 29 and Day 57. The concentration at 12-hour time point will be assumed to be the same as the pre-dose level.

Plasma PK parameters will be calculated by standard non-compartmental analysis. The actual collection times will be used for PK parameter calculation. The linear trapezoidal rule method (equivalent to the Linear Trapezoidal Linear Interpolation in WinNonlin® Professional) will be used in the computation of AUCs.

PK parameters will be listed and summarized descriptively.

### 3.6 Safety Assessment

Safety data will be summarized based on the Safety Population.

#### 3.6.1 Adverse Events (AEs)

AEs will be captured from the first dose of study drug and SAEs will be captured from the date of informed consent through study completion and summarized overall. All AEs will be coded to system organ class (SOC) and preferred term (PT) using Medical Dictionary for Regulatory Activities (MedDRA) version 20.1. Treatment-emergent adverse events (TEAEs) are defined as AEs that start after the first dose of study drug.

An overview of AEs will be provided including counts and percentages of subjects (and event counts) with the following:

- Any TEAEs (overall and by maximum severity)
- Any study drug related TEAEs (overall and by maximum severity)
- Any serious AEs (SAEs)
- Any treatment-emergent serious AEs (TESEAEs)
- Any TEAEs leading to discontinuation of study drug
- Any TEAEs leading to discontinuation of study
- Any AEs leading to death

All adverse events will be listed by subject including TEAE status (Yes/No), MedDRA SOC, PT, verbatim term, AE start/stop day, severity, relationship to study drug, action taken with study treatment, outcome, and SAE categories (if applicable).

### 3.6.2 Clinical Laboratory Tests

Blood and urine samples for clinical laboratory tests will be collected at Screening, Day 1, Day 15, Day 29, Day 57, Day 85 (Week 12), Week 16, Week 20, Week 24, Week 28, Week 32, Week 36, Week 40, Week 44, Week 48, Week 52, Early Termination (if applicable), and follow-up visit. Midstream spot urine void for UPCR during the site visits will be collected at every timepoint during the study. All chemistry, hematology, and urinalysis tests will be processed by a central laboratory. Local laboratory data will be listed.

### 3.6.3 Vital Signs

Vital signs will be measured at every study visit during the Treatment Period and Extension Period. Vital sign parameter values will be listed by subject at each visit.

### 3.6.4 Electrocardiograms

Triplet 12-lead ECGs will be taken at Screening, Day 1, Day 29, Day 57, Day 85 (Week 12), Week 16, Week 20, Week 24, Week 28, Week 32, Week 36, Week 40, Week 44, Week 48, Week 52/Early Termination, and follow-up. ECG parameter values will be listed by subject at each visit.

### 3.6.5 Physical Examinations

Physical examination abnormalities will be listed by subject.

### 3.6.6 AIDS Clinical Trials Group – Brief Peripheral Neuropathy Screening Tool (ACTG BPNST)

ACTG-BPNST results will be listed by subject at each visit.

## 4 DATA MONITORING COMMITTEE

Due to the unblinded nature of the study, a Data Monitoring Committee (DMC) was not utilized for this study. However, a Study Review Committee as described in the protocol was convened to review efficacy and safety data.

## 5 ANALYSIS TIMING

### 5.1 Interim Analysis

No interim analysis is planned.

